9.3.2 ANALYSIS OF THE SECONDARY ENDPOINT

The secondary endpoints will be defined as

- Comparative assessment of seroprevalence via PRNT50 titers for ZIKV, DENV, and CHIKV in Cambodian adults and macaques to that of Thai adults and macaques.
- Assessment of reactivity to salivary gland homogenate of *Aedes aegypti* as detected by ELISA or western blot in human and macaque sera.

Differences in seroprevalence will be assessed via a two-sample test of binomial proportions, treating participants and each study sample as mutually independent of one another. Pairwise comparisons of PRNT50 titers as continuous variables will be assessed via Wilcoxon rank sum tests as follows: Thai adults versus Cambodian adults, Thai macaques versus Cambodian macaques, and Thai adults and macaques versus Cambodian adults and macaques.

For salivary gland reactivity, arbitrary ELISA units as a continuous variable will be assessed and categories will be made for high, medium, low, and negligible reactivity to salivary gland homogenate. These categories will be compared as: Thai adults versus Cambodian adults, Thai macaques versus Cambodian macaques, and Thai adults and macaques versus Cambodian adults and macaques. Regression models fit via generalized estimating equations will be used to assess if higher antibody reactivity is associated with PRNT50 titer and positive/negative seroprevalence of ZIKV, DENV, or CHIKV.

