For activities in Thailand, a separate IRB application, protocol, and consent form per Thai standards was submitted and approved by the Mahidol University IRB. The macaque sampling in Thailand was performed in 2018 and human sampling was performed from September 2019 through March 2020. A copy of the Thai IRB approval will be included with this protocol for NECHR. A Materials Transfer Agreement will be in place prior to sharing of data and serological materials between Cambodia and Thailand portions of the study.

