We aim to conduct a similar prospective serosurvey in Cambodia, sampling both human and macaque populations living in proximity to one another within the same season. Macaques were chosen because they are ubiquitous in moderately to heavily human-populated areas around Asia and tend to have heavy human interaction in tourist areas. This means that the possibility for transmission is likely, as they overlap with the human population. This is relevant not only because the macaque could act as a spill-over vector into the human population, but also if there is no ZIKV in Cambodia, it is likely that it will be introduced in heavily touristed areas, meaning there is the potential to establish both anthroponotic and sylvatic cycles. Cambodian macaque serum samples will be collected separately by Thai and Cambodian veterinarians as approved by the Cambodian Ministry of Agriculture, Forestry, and Fisheries, specifically the Director General of Animal Health, within a year of this human study in Cambodia.

An arboviral pediatric cohort study (NIH protocol 18-I-N100, “Investigating vector-borne determinants of *Aedes*-transmitted arboviral infections in Cambodia: an observational longitudinal cohort study in children”) is already established by NIAID in a peri-urban area of Kampong Speu province, known for 2 other *Aedes*-transmitted viruses, DENV and CHIKV (Figure 1). Therefore, we propose to prospectively collect sera from long-tailed macaques at Wat Amphae Phnom in Kampong Speu, Cambodia and nearby adults for comparison with sera sampling performed in Thai macaques and nearby villagers.

Figure 1. Cambodia Sampling Map

Left: Blue circle represents Chbar Mon town in Kampong Speu province (in red).

Right: Red circle represents Wat Amphae Phnom and H designates hospital in Chbar Mon town.

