5.5 STRATEGIES FOR RECRUITMENT AND RETENTION

Advertising and recruitment in this province will mainly be via word-of-mouth using provincial health staff and the local village chiefs to communicate to people living and working near Wat Amphae Phnom.

For this biospecimen procurement protocol, we anticipate having to screen no more than 350 to enroll our goal number of 300 participants over the study period. We have no pre-set male:female ratios or age structures.

The anticipated length of individual study participation is limited solely to that time of blood draw and baseline assessments.

Lastly, the typical cost of reimbursement from a blood draw in Cambodia is \$5 US (to be paid in Cambodian Riel). We will adhere to this guideline for recruitment and reimburse participants in cash.

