8 STUDY ASSESSMENTS AND PROCEDURES

8.1 CLINICAL EVALUATIONS

- **Screening (Day 0):** Prior to conducting any study-related procedures, informed consent in Khmer will be obtained from the participant via in-person interview with an investigator. If illiterate, a literate witness will read and sign the informed consent on behalf of the participant, and the participant will provide a thumbprint. The participant will be queried regarding a history of significant medical disorders and other eligibility criteria. A screening log will be kept to document eligibility of all participants.
- **Enrollment/Visit 1/Exit (Day 0): Baseline Assessments**
 - Baseline demographics will be collected such as sex, age, and behaviors related to vector-borne disease development (e.g., number of domestic water containers), including recent travel and extent of interactions with the macaques.

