9.3 STATISTICAL ANALYSIS

9.3.1 ANALYSIS OF THE PRIMARY ENDPOINT

The primary endpoint will be defined as:

- Assessment of seroprevalence via screening ELISA and/or PRNT50 titers for ZIKV, DENV, and CHIKV in Cambodian adults.
- Assessment of seroprevalence via screening ELISA and/or PRNT50 titers for ZIKV, DENV, and CHIKV in Cambodian macaques as compared to humans.

PRNT50 titer is a continuous variable (e.g., 0 to 40960) as measured from human and macaque sera at a single timepoint. For the purpose of classifying an individual as positive for a particular arbovirus, a PRNT50 titer of 50 will be taken to indicate that an individual has seroconverted (based on distribution of assay, we can consider <10 as seronegative, 10-50 as indeterminate, and >50 as seroconverted). We will estimate seroprevalence rates for humans and macaques, and report summary statistics of seroprevalence and titer distributions overall and within meaningful subgroups (e.g., males vs. females, by decade of age, by occupation, by bed net use, by intensity of self-reported interaction and duration with macaques).

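### The human Thai-Cambodian comparison has no age-adjusted analysis, so a difference in age mix could bias it wherever seroprevalence rises with age (most plausibly dengue)

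*Combined protocol and SAP*

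**What the plan says.** Section 9.3.2 sets out the country comparison: "Differences in seroprevalence will be assessed via a two-sample test of binomial proportions". For titers it says "Pairwise comparisons of PRNT50 titers as continuous variables will be assessed via Wilcoxon rank sum tests as follows", and lists Thai against Cambodian adults among the pairs. Neither test is adjusted. The section's only regression, by generalized estimating equations, relates salivary antibody reactivity to titer and serostatus and is not described as a country comparison.

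Age is available in Cambodia. Section 8.1 says "Baseline demographics will be collected such as sex, age, and behaviors related to vector-borne disease development". In the analysis it appears only in Section 9.3.1, which will "report summary statistics of seroprevalence and titer distributions overall and within meaningful subgroups", with decade of age as one example.

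Nothing in the design balances age between countries:
- Section 5.1 admits Cambodians aged 18-55, and Section 5.5 says "We have no pre-set male:female ratios or age structures". It also says "Advertising and recruitment in this province will mainly be via word-of-mouth using provincial health staff and the local village chiefs".
- For Thailand, the Statement of Compliance says "a separate IRB application, protocol, and consent form per Thai standards was submitted". Section 2.2 describes the contrast as "nearby adults for comparison with sera sampling performed in Thai macaques and nearby villagers". The age limits and age mix of the Thai adults are not given.

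**The concern.** Country is not randomised here, and the endpoint is cumulative: Section 7.4 says the study looks at past exposure, and Section 2.2 names IgG. Under sustained transmission older adults have had more years in which to be infected. If one country's volunteers are older, its crude seroprevalence is higher even when infection risk at each age is the same.

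The three viruses differ in how far the documents support an age gradient:
- **DENV:** Section 9.2 calls it hyperendemic in both countries and long endemic. An age gradient is most plausible here.
- **CHIKV:** Section 9.2 describes sporadic, focal transmission. A gradient is possible.
- **ZIKV:** Section 9.2 says active detection is recent, while the title of reference 3 speaks of long-term circulation in Thailand. The exposure window is left open.

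All three country contrasts are secondary endpoints and use the same crude test. At stake is whether a reported country difference, or its absence, reflects the country or the age of the volunteers.

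**Working it through.** **1. The plan's own figure.** Section 9.2 gives 50% against 37%, 300 per country, alpha 0.05 and 90% power. Sidedness is not stated; two-sided is assumed.
- Pooled SE = sqrt(2 × 0.435 × 0.565 / 300) = 0.0405.
- SE under the alternative = sqrt((0.50 × 0.50 + 0.37 × 0.63) / 300) = 0.0401.
- Power = Φ((0.13 − 1.96 × 0.0405) / 0.0401) = Φ(1.26) = 89.7%.

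The stated 90% reproduces for an unadjusted comparison.

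**2. Model for the age effect (all assumptions).** Prevalence at age a is p(a) = 1 − exp(−λ · min(a, T)), where T is years since transmission began. λ is set so that prevalence at age 36.5 equals a chosen anchor. Ages have SD 9, clipped to 18-55, with country means 36.5 ± half the gap. There are 300 per country, no true country effect, and 6000 replicates (Monte Carlo SE about 0.3 points at 5%).

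Tests compared:
- Crude: z = (p1 − p2) / sqrt(2 · p̄(1 − p̄) / 300).
- Mantel-Haenszel over ages 18-24, 25-34, 35-44 and 45-55: z = Σ(x1k − n1k·mk/Nk) / sqrt(Σ n1k·n2k·mk(Nk − mk) / (Nk²(Nk − 1))).

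Hand check at 50%, lifelong exposure: λ = ln 2 / 36.5 = 0.0190. The slope at 36.5 is 0.0190 × 0.5 = 0.0095 per year, so a 5-year gap gives about 4.75 points. The simulation gives 4.60, slightly less because ages are clipped.

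**3. Lifelong exposure, no true difference.**

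| Prevalence at 36.5 | 3-year gap: spurious points / crude rejection | 5-year gap: spurious points / crude rejection |
|---|---|---|
| 50% | 2.76 / 10.9% | 4.60 / 20.6% |
| 70% | 2.94 / 12.1% | 4.90 / 26.1% |
| 80% | 2.71 / 12.6% | 4.50 / 27.3% |
| 90% | 2.06 / 11.9% | 3.45 / 25.9% |
| 95% | 1.47 / 11.3% | 2.43 / 23.7% |
| 98% | 0.88 / 9.4% | 1.47 / 17.9% |

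At a 2-year gap the crude rate is 7-9%. With no gap it is 4.7-5.8%. Mantel-Haenszel stays at 4.1-5.9% in every scenario.

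A calculation with a different age shape (exponentially tilted, means 39 and 34, λ = 0.02) gives 53.1% against 48.2% and crude rejection of 22%, in line with the 50% row.

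**4. Shorter exposure, prevalence 50%.** Crude rejection at 3- and 5-year gaps:
- T = 40: 8.3% and 13.6%
- T = 30: 5.5% and 6.9%
- T = 25: 5.3% and 5.3%
- T = 20: 5.0% and 5.0%

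The reason is simple: with T = 20, everyone aged 20 or over has had the same exposure time.

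**5. Masking of a true ZIKV difference (Cambodian sample older).** Power for 50% against 37%, crude / Mantel-Haenszel:

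| Gap | Lifelong | T = 20 |
|---|---|---|
| 0 | 88.1% / 88.3% | 90.0% / 89.5% |
| 3 years | 71.8% / 86.2% | 89.6% / 88.5% |
| 5 years | 57.3% / 84.2% | 89.1% / 87.0% |
| 10 years | 19.8% / 74.3% | 88.6% / 80.4% |

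Section 9.2 centres its precision calculation for Cambodia on 5%. At 50% against 5%, crude power is 100% at every gap from 0 to 10 years, even with lifelong exposure.

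**6. Titers** (0 if negative, lognormal if positive, 2000 replicates). Wilcoxon rejection at 3 and 5 years is 9.7% and 19.7% (50%, lifelong), 8.3% and 15.1% (80%, lifelong), and 5.7% and 5.0% (50%, T = 20). A van Elteren test by decade of age stays at 4.3-5.9%.

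**The case against.** **No age gap is shown.** This stands. The Thai ages belong to a protocol not available here, and with equal age mixes there is no bias. Section 4.2 speaks of a multisite study of people aged 18-55, which might suggest common limits. It also places all enrollment in Cambodia, and common limits would not make the age mix equal. A reader might infer that the planned comparison is biased; the documents support only that it is unprotected.

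**The only stated hypothesis and the only powered human comparison concern ZIKV.** This limits the point. A reader might infer that the 90% power is wrong or that age could hide the expected ZIKV difference. The power reproduces. Masking needs both long-standing transmission and a Cambodian prevalence near 37%. That value matches the 37.3% equivocal results that Section 9.2 attributes to a potentially cross-reactive assay. The evidence for long-standing transmission is one reference title, which gives no number of years.

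**Dengue may be near saturation.** Saturation shrinks the bias in points (0.88-1.47 at 98%) but does not restore the 5% error rate (9.4-17.9%).

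**The decade-of-age summaries already help.** In part. Made for both human samples, they would expose an imbalance. They would not change the test or give an adjusted difference, and an adjustment chosen after seeing them would not be pre-specified.

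**Country is confounded with site anyway.** True. Age adjustment removes only one source of non-comparability.

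**Conclusion.** The omission is real and worth correcting as an inexpensive safeguard; it is not a demonstrated error. Under constant lifelong infection risk and prevalence of 50-98%, a 3-year gap in mean age would create a spurious difference of 0.9-2.9 points and a 5-year gap 1.5-4.9 points. The crude false-positive rates would be 9-13% and 18-27%, against about 5% for the stratified test. The gaps and the gradient are assumptions; the documents give neither Thai ages nor age-specific seroprevalence, so the actual size and direction are unknown.

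The point applies most clearly to DENV and possibly to CHIKV. For ZIKV it matters only if transmission is older than about 25 years. The absence of bias at 20 years or less is a result of this model, not a fact about the sites.

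**What to change.** In Section 9.3.2, for the human comparison:
- Keep the crude binomial test, and tabulate age and sex of both human samples beside it.
- For each virus, pre-specify one age-stratified comparison, Mantel-Haenszel by decade of age, whatever prevalence is observed. Making the method depend on the observed prevalence would undercut pre-specification.
- Report the prevalence difference with a 95% CI, standardised to the pooled age distribution of the two human samples.
- For titers, use a van Elteren test by decade of age.
- State in advance that the age-stratified result is the one interpreted as the country difference if the two disagree.

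The cost is SAP wording, a little more analysis, and confirmation that individual Thai ages exist. With equal age mixes the power cost is negligible (90.0% crude, 89.5% stratified at T = 20). If age mixes differ but seroprevalence does not rise with age, the loss is about 1 point at a 3-year gap, 2 points at 5 years and 8 points at 10 years. The change does not address other site differences, or the macaque and pooled human-macaque contrasts.

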4 STUDY DESIGN

4.1 SITE DESCRIPTION

Located in Cambodia, the main town of Chbar Mon (estimated population approximately 55,000-60,000 over 10 km²) is located 44 km from Phnom Penh city center. Chbar Mon is the largest operational district in Kampong Speu province and is the site of the Kampong Speu District Referral Hospital, a hospital of approximately 120 beds with 130 staff of medical doctors, nurses, and lab technicians. NIAID has a field house behind the hospital that serves as an office and temporary clinic when needed.

Wat Amphae Phnom is a pagoda next to a river tributary of the Mekong with 3 different macaque troops, numbering over 75 to 100 per troop. Similar to the sites in Thailand, the pagoda is a popular tourist destination where locals purchase food from vendors to feed the monkeys and also hosts a local marketplace and restaurants (called Resort Amphae Phnom). Over 100 monks also live at the pagoda. The closest residences are in the section of town called Taing Toun Le, where NIAID already has many children enrolled in a healthy pediatric cohort.

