5 STUDY POPULATION

5.1 INCLUSION CRITERIA

In order to be eligible to participate in this study, an individual must meet all of the following criteria:

1. Provision of signed and dated ICF
2. Able to provide informed consent
3. Stated willingness to comply with study procedures
4. Male or female, aged 18-55 years
5. Live/work within approximately 10 km of the Wat Amphae Phnom monkey habitat for minimum of 2 years
6. In good general health as evidenced by screening medical history
7. Willing to allow biological samples to be stored for future research

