7.2 PROCEDURES

Screening (Day 0):

The enrollment will take place in or near the pagoda or other appropriate location as has been done for prior NIAID studies in Kampong Speu using privacy screens, tables, and chairs that are typically set up within the main rooms of the pagoda. The following procedures will be performed:

- Informed consent
- Review of inclusion/exclusion criteria

Enrollment (Day 0):

- Baseline assessments and risk factors
- Blood draw

Any participant who experiences complications due to phlebotomy will be examined by the physician onsite or referred to the hospital and followed until complications have resolved and/or referral to the necessary medical care has been made.

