With regards to the sample size in humans, Thailand and Cambodia have both been endemic for dengue for many years. Only recently has ZIKV been actively detected in both countries.^{18,22-24} In Thailand, a serosurvey in a sample of 21 humans estimated ZIKV seroprevalence to be 76% (95% CI: 52%, 91%).²⁵ Another survey of 600 migrant workers from four Southeast Asian countries, 150 of whom were from Thailand, estimated overall seroprevalence to be 38.8% and seroprevalence among the Thai cohort to be 50.7%.²⁶ However, in Cambodia, the estimated seroprevalence was lower, estimated to be <1% definitively with 37.3% equivocal results.⁸ These equivocal results were based on a potentially cross-reactive IgM assay and indicated a recent flavivirus infection with either Japanese encephalitis virus (JEV), DENV, or ZIKV. Treating sampled humans as mutually independent simple random samples of binary responses for seropositivity, a sample of 300 humans in Cambodia will yield an average 95% CI width of less than or equal to 0.052 for presumed seroprevalence centered at 0.05 (Figure 2).

Our secondary objective is to compare human ZIKV seroprevalence in Cambodia with ZIKV seroprevalence in Thailand. Conservatively taking a value of 50% seroprevalence for ZIKV in Thailand and 37% seroprevalence in Cambodia, we calculate that a sample size of N=300 Cambodian participants and N=300 Thai participants will be sufficient to attain 90% power to reject a null hypothesis of no difference in seroprevalence using a binomial test of proportions with a Type-1 error rate of 0.05.

[figure not shown]

Figure 2. Expected precision of seroprevalence estimate versus sample size and true seroprevalence

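### The human seroprevalence test, interval width and power assume independent participants, but word-of-mouth recruitment through village chiefs may enrol household or village members together, and no group field or clustered variance is stated

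*Combined protocol and SAP*

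**What the plan says.** Section 9.3.2 compares human seroprevalence with a two-sample binomial test, "treating participants and each study sample as mutually independent of one another". Section 9.2 derives the expected interval width of 0.052 (300 Cambodian adults, prevalence 5%) by "Treating sampled humans as mutually independent simple random samples of binary responses for seropositivity". It then calls 300 Cambodian and 300 Thai participants "sufficient to attain 90% power to reject a null hypothesis of no difference in seroprevalence using a binomial test of proportions", taking 50% in Thailand and 37% in Cambodia at a type I error of 0.05. That sentence does not repeat the independence condition.

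On how people come in, section 5.5 says recruitment will "mainly be via word-of-mouth using provincial health staff and the local village chiefs". Section 7.2 says "The enrollment will take place in or near the pagoda or other appropriate location". The geographic criterion in section 5.1 is "Live/work within approximately 10 km of the Wat Amphae Phnom monkey habitat for minimum of 2 years". Neither 5.1 nor 5.2 limits enrolment to one person per household, and no probability sampling is described.

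The only method for correlated data is in section 9.3.2: "Regression models fit via generalized estimating equations will be used to assess if higher antibody reactivity is associated with PRNT50 titer". It applies to the salivary-reactivity regression and has no stated cluster unit. The baseline items in section 8.1 and the subgroups in 9.3.1 name no household or village identifier, although the list in 8.1 is illustrative.

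The synopsis gives one site in Cambodia, while sections 4.1 and 9.2 refer to Thai sites in the plural. The hypothesis in 9.1 and the first secondary objective are worded by country.

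**The concern.** Recruitment through village chiefs and personal contact is a natural way to enrol several members of one household or hamlet. The plan itself gives reasons to expect shared exposure: section 8.1 collects the number of domestic water containers, which housemates have in common, and section 9.2 describes chikungunya transmission as highly focal. If serostatus is positively correlated within enrolled groups, 300 people carry less information than 300 independent people.

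The Thai-Cambodian test would then reject a true null more than 5% of the time, the 90% power would be overstated, and the seroprevalence intervals could undercover. Those intervals describe the first primary endpoint. Without a coded group field in the analysis data, a correction cannot be made directly.

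A separate matter of wording follows from the design. With one Cambodian site, a site difference cannot be told apart from a country difference on that side, and no variance correction changes this.

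**Working it through.** **Inputs from the documents.** 300 per country, 50% versus 37%, type I error 0.05, power 90%; width at most 0.052 at n = 300 and prevalence 5% (all section 9.2). Sidedness is not stated; two-sided reproduces the figure.

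**Inputs assumed.** The documents give no intraclass correlation (ICC), group size or design effect (DE). I use DE = 1.05, 1.1, 1.25, 1.5 and 2.

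**Step 1: reproduce the plan's power.** The pooled proportion is 0.435.
- SE under the null: √(0.435 × 0.565 × 2/300) = 0.0405
- SE under the alternative: √((0.50 × 0.50 + 0.37 × 0.63)/300) = 0.0401
- Power = Φ((0.13 − 1.96 × 0.0405)/0.0401) = 89.7%

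This matches 90%, so the stated power contains no allowance for clustering.

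**Step 2: reproduce the plan's width.** The mean exact (Clopper-Pearson) width over Binomial(300, 0.05) is 0.0524, which rounds to 0.052. The Wald width, 2 × 1.96 × √(0.05 × 0.95/300), is 0.049. The exact interval is therefore the one that matches.

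**Step 3: apply the design effects.**
- Type I error of the planned test, both samples clustered: 2 × (1 − Φ(1.96/√DE))
- Type I error, Cambodia only: the same with (1 + DE)/2 in place of DE
- Power of a correctly sized test: step 1 with 300/DE in the clustered sample or samples
- Exact width: mean Clopper-Pearson width at n = 300/DE, prevalence 5%

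| DE | Type I, both | Type I, Cambodia only | Power, both | Power, Cambodia only | Exact width at 5% |
|---|---|---|---|---|---|
| 1 | 5.0% | 5.0% | 89.7% | 89.7% | 0.052 |
| 1.05 | 5.6% | 5.3% | 88% | 89% | 0.054 |
| 1.1 | 6.2% | 5.6% | 87% | 88% | 0.055 |
| 1.25 | 8.0% | 6.5% | 82% | 86% | 0.059 |
| 1.5 | 11.0% | 8.0% | 75% | 82% | 0.065 |
| 2 | 16.6% | 11.0% | 62% | 75% | 0.076 |

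With both samples clustered, power drops below 80% at a DE of about 1.32.

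**Step 4: what would produce these values.** DE = 1 + (m − 1) × ICC for m people per group.
- Two per household, ICC 0.05 to 0.10: 1.05 to 1.10
- Three per household, ICC 0.125 to 0.5: 1.25 to 2

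**Step 5: coverage of the exact 95% interval computed under independence.** Simulated with beta-binomial households of these sizes, n = 300, at the five DEs in order:
- At 5% prevalence: about 96, 96, 94, 92 and 87% (about 97% with no clustering)
- At 37% prevalence: about 94, 94, 92, 90 and 84%

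**Step 6: sensitivity of power to the true gap.** At 50% versus 30%, 90% power is kept up to a DE of about 2.4. At 50% versus 5%, power is still near 100% at DE 2.

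**The case against.** The independence assumption is disclosed, and nothing in the documents shows that it fails by a material amount. This stands: every design effect above is assumed, and the simplest household scenario gives only 5.6% to 6.2% type I error and 88% to 87% power.

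The power loss also depends on the 50% versus 37% contrast, which the plan calls conservative. This stands too, but a wide gap does not protect type I error or interval coverage.

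Three stronger readings are tempting and are not supported.

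- A reader might take the line "Over 100 monks also live at the pagoda" as evidence of a large cluster that inflates the variance. A monastery included by design is better handled as a stratum, and the same holds for villages if all of them are covered. The case rests mainly on households, and on villages only if they enter as a sample.
- A reader might infer that the primary intervals must be too narrow. At 5% prevalence the exact interval is conservative enough to stay at about 94% or above up to a design effect of 1.25. Section 9.3.1 names no interval method, so the answer depends on the method and the prevalence.
- A reader might infer that clustering could never be examined. The baseline list in 8.1 is open, the case report form is not among the documents, and section 10.1.3 says contact information and linking logs are kept. Authorised staff could derive coded groups. Section 10.1.7.1 withholds names and identifiers from analysis staff, which does not rule out a coded group number.

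**Conclusion.** The point holds as a conditional one. The plan assumes independence for the human test, width and power, describes recruitment that does not secure it, and states no group field or clustered variance for these analyses. If household or village members enrol together and their serostatus is positively correlated, the planned test is anti-conservative and the 90% power is optimistic. The effect is slight at design effects of 1.05 to 1.1 and serious at 1.5 to 2; the documents do not say where the study will fall.

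The country wording goes beyond the design on the Cambodian side only, since the Thai sites are plural. No error is claimed in the macaque power, and the reporting of macaque troops is outside this point.

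**What to change.** 1. Confirm that the Cambodian case report form holds a household and a village field, or add them, as coded numbers so that section 10.1.7.1 is respected. There is a single visit and no follow-up, so that visit is the easiest time to record them.
2. In 9.3.1 and 9.3.2, compute the human seroprevalence intervals and the Thai-Cambodian test with a variance clustered on household, with villages or the monastery as strata where they are fully covered. If about one person per household enrols, the result will be close to the planned one. Where Thai identifiers do not exist, give a sensitivity analysis over Thai design effects of 1 to 2.
3. In 9.2, state that the 90% power also assumes independence, and show power and interval width over design effects 1 to 2.
4. Word the hypothesis in 9.1 and the secondary conclusion as a comparison of the sampled Cambodian site with the sampled Thai sites.

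The cost is a few form fields, slightly wider intervals, less favourable stated power and a narrower conclusion. Thai sampling was done under a separate protocol, so that half may remain a sensitivity analysis. None of this repairs selection bias from word-of-mouth recruitment.
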